#### 3. Data extraction and models

One year of data will be extracted from each of the 46 centres taking part using an NBSS report developed by [name] at Acamdex, based on the trial tables in NBSS developed by Temenos Ltd. Data extraction will be 8 weeks after the one year is complete, to allow time for women to be recalled for further tests and the results entered into the database. Levels of missing data will be assessed, and a follow up data extraction may be performed. This would be achieved by re-extracting the entire dataset.

One line of data will be extracted for each woman who attended screening during the data collection period.

The following data items will be collected for each woman. Italicised text in square brackets indicates NBSS variables that will be extracted.

#### Possible levels in model

The following variables will be used to construct a multi-level model (see section 6 for more details).

- Centre ID
- Batch ID
- Woman ID

## Model predictors from NBSS

The following variables will be used to construct a multi-level model (see section 6 for more details).

- Trial arm: Intervention or Control [TrialArm Intervention = FR and RF, Control = FF and RR] Trial assistant to blind the dataset before analysis by [name]. TrialArm to be replaced by condition 1 and condition 2. Case order columns to be removed, leaving only whether each case was read in the intended order.
- Woman's age at screening
- Prevalent or incident screen

### Subgroups for subgroup analysis

The following variables will be used to construct subgroups for analysis (see section 8 for more details).

- Woman's age in groups: 52 and under, 53-59, 60 and over
- Case position in batch [number of cases from either the beginning or end of the batch, whichever is smaller], with extra column dichotomising into 'first or last five' and 'other'.
- Whether the batch was read first in a workday by both readers [calculated by whether another batch was read by the same reader that day for both readers]

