#### 1.2 Existing knowledge

In the NHSBSP, each set of mammograms is read by two radiologists who each indicate if there should be a recall for further tests. Disagreements are referred for arbitration, usually by a third radiologist. Radiologists assess two mammograms per minute on average which equates to 120 in a 1-hour session. This is a highly skilled, pressurised but repetitive and frequently intellectually unchallenging activity. A vigilance decrement of performance decrease over time has been observed in similar repetitive visual tasks such as radar operator.

Data from an observational study using the Breast Screening Programme database for eight English breast screening centres for 3 years has shown that the probability of being recalled for further tests and of having cancer detected at screening is dependent on the time since the radiologist had a break from reading. For the first ten cases after a first reader break, the cancer detection rate for the whole process (including second reader and arbitration) is higher. These extra cancers detected are not associated with a higher probability of being DCIS rather than invasive, and have a similar mix of grades 1, 2 and 3 to the rest of the cancers detected at screening so this phenomenon is unlikely to be associated with increased overdiagnosis.

First and second readers read each batch of mammograms in the same order, thus their postbreak increases in cancer detection rate occur when reading the same women's mammograms.

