## 1.3 Hypothesis

If the second radiologist examines the batch of mammograms in the reverse order to the first radiologist this will increase the overall cancer detection rates, because each radiologist's peak performance will be when examining different cases.

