#### 1.4 Need for a Trial

A previous observational study has shown a reduction in sensitivity with a proxy for time (number of cases) since a break. Currently both radiologists are presented with cases in the same order as one another, so both have reduced sensitivity when reading the same cases. Therefore changing the order in which the second radiologist is presented with the mammograms may increase sensitivity of screening. A trial is required to determine whether such improvements would be realised in practice.

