## 3.4 Statistical Analysis Plan

## i) Primary

To determine whether cancer detection rate is higher in the intervention group in comparison to the control group analysis will be conducted using a multi-level logistic regression model.

Levels to be included in the model are case, batch, and centre. To prevent over-fitting each level will only be included if they explain a sufficient portion of the variability.

It is reasonable to expect characteristics at the level of the women screened to be very similar between intervention and control due to the large number of batches of women randomised. Similarly centre level characteristics such as the arbitration system used will not differ between intervention and control as randomisation is at the batch level within each centre. Therefore the main analysis will simply contain one predictor, intervention or control arm. The intervention will be considered effective if the 5th percentile of the distribution of the coefficient for the intervention in the model is greater than zero.

A second analysis will be conducted including adjustment for characteristics of the woman screened (age and whether they have previously attended screening). Sub-group analysis will be conducted in younger women, those whose cases are read at the beginning or end of the batch, and younger women, as the intervention may be more effective in these groups.

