#### Analysis 1:

The first model will include only treatment as a predictor of cancer detection. Levels considered for inclusion in the model will be: case; batch; and centre. To prevent over-fitting, each level will only be included in the final model if it explains a sufficient portion of the variability and improves model fit. Screening centre will be added as a level to the model to account for clustering. It will be retained in the model if it improves model fit (Wald test at the 5% level, see limitations section). Then batch will be considered for addition as a level to this model if it improves model fit according to the same criteria. The treatment will be added to this model.

A sub-analysis of those cases which are intended to be read in the first or last 5 of the batch, younger women  $(\le 52, 53-59, \ge 60)$  and the first batches to be read in a workday (by both readers) will be conducted.

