#### Analysis 3:

This is exploratory follow-up analysis but will not form part of the analysis in the main paper

The third model will be used to determine whether there are particular circumstances in which the intervention is effective.

Predictors to be considered for inclusion will be added separately as fixed effects to the baseline model from analysis 2. Those predictors which improve the model (Wald statistic sig at 10% level) will be added to one model, with those with highest Wald statistic added first. Those for which the Wald statistic remains significant at the 10% level will be retained in the baseline model. Predictors to be considered for inclusion are number of readers involved in arbitration (categorical: 1/2/3 or more), arbitration policy (binary: all recalled cases arbitrated/disagreements only arbitrated), arbitration independence (same/ different readers read and arbitrate the case) whether reader 2 can see reader 1 opinion (categorical: yes on computer/yes but only on paperwork/no), how the mammograms from the previous screening round are displayed (categorical: digital/film pre-hung on a multi-viewer/film available in bag by the workstation), whether the batch was read immediately after another batch(categorical no/yes one reader/yes both readers), the number of cases in the batch, and where in the batch the case was intended to be read (number of cases from beginning/end).

The treatment will be added to this model. The interaction between treatment (intervention or control) and each of these predictors will then be considered for inclusion using the same process and criteria.

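### The position subgroup pools both ends of the batch, so it tests the net gain there but only weakly tests the mechanism; an arm-by-reader-1-position term should be added

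*Combined protocol and SAP*

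**What the plan says.** - **Mechanism.** Protocol 1.2 reports that in the first ten cases after a first-reader break "the cancer detection rate for the whole process (including second reader and arbitration) is higher", and that both readers currently follow the same order. Protocol 1.4 adds the other half: "so both have reduced sensitivity when reading the same cases". Under reversal, Protocol 1.3 expects that "each radiologist's peak performance will be when examining different cases".
- **Subgroup and its reason.** Protocol 3.4 (Primary) names "those whose cases are read at the beginning or end of the batch" as a subgroup, "as the intervention may be more effective in these groups".
- **Definition.** SAP section 3 (Subgroups) uses "Case position in batch [number of cases from either the beginning or end of the batch, whichever is smaller", with a further column separating the five cases at either end from the rest.
- **Use.** SAP section 6, Analysis 1: "A sub-analysis of those cases which are intended to be read in the first or last 5 of the batch". Analysis 3, which is exploratory and outside the main paper, considers "where in the batch the case was intended to be read (number of cases from beginning/end") as a predictor and for interaction with treatment. Neither names the reader whose order counts.
- **Arms and blinding.** SAP section 3 (Model predictors) defines intervention as FR and RF and control as FF and RR. It removes the case order columns before the blinded analysis.
- **Unfolded order elsewhere.** Protocol 3.3, secondary outcome 4, and SAP section 8 (R1intendedOrder) look at performance along the reading order. Neither specifies a comparison of arms by order.

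**The concern.** The mechanism does not predict the same arm effect at both ends of reader 1's sequence. Where reader 1 is early, the control arm has two fresh readers and the intervention arm one, so reversal should cost detections. Where reader 1 is late, control has none and intervention has one, so reversal should gain detections. A measure based on distance to the nearer end averages a predicted loss with a predicted gain.

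What is at stake is the secondary aim in Protocol 3.2 of investigating how the intervention works. The direct sign that reversal moved the readers' peaks is the contrast between the two ends. The fold removes that contrast, and no other planned analysis restores it.

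**Working it through.** **1. The plan's own scale.** The documents give no figure for the position subgroup. Their effect size is 7.8 versus 8.3 per 1000, two-sided 5%, 80% power. The usual two-proportion formula gives 501,398 per arm, against 501,361 stated. Then 2 × 501,361 × 1.09 = 1,092,967, against 1,093,780 stated. (The SAP's design-effect formula gives 1 + 39 × 0.002 = 1.078 rather than 1.09; this does not affect the present point.)

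**2. Fresh readers per case, by reader 1's position.**

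| Reader 1 reads the case | Control (FF, RR) | Intervention (FR, RF) |
|---|---|---|
| early | 2 fresh | 1 fresh |
| late | 0 fresh | 1 fresh |

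**3. Formulas.** Assume independent reads, detection if either reader sees the cancer, and single-reader sensitivity h when fresh and l when tired.
- Control early: 1 − (1−h)². Control late: 1 − (1−l)². Intervention at both ends: 1 − (1−h)(1−l).
- Arm effect early: −(1−h)(h−l).
- Arm effect late: +(1−l)(h−l).
- Folded average: (h−l)²/2.
- Share of the gain offset by the loss: (1−h)/(1−l).

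The signs are opposite for every l < h < 1. The folded effect is never negative and is always less than half the late gain.

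**4. Numbers.** The documents give no values for h or l, so these are assumptions (effects in percentage points of sensitivity).

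| h / l | Early | Late | Folded | Gain offset |
|---|---|---|---|---|
| 0.75 / 0.70 | −1.25 | +1.50 | +0.13 | 83% |
| 0.80 / 0.70 | −2.0 | +3.0 | +0.5 | 67% |
| 0.85 / 0.75 | −1.5 | +2.5 | +0.5 | 60% |
| 0.90 / 0.80 | −1.0 | +2.0 | +0.5 | 50% |
| 0.90 / 0.70 | −2.0 | +6.0 | +2.0 | 33% |
| 0.95 / 0.75 | −1.0 | +5.0 | +2.0 | 20% |

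**5. Gaps that would produce the planned effect.** Take total cancers C as 7.8 plus the interval rates in Protocol 1.1 (2.3 or 3.7), so 10.1 or 11.5 per 1000. Let f be the share of cases affected, assumed to be 25% to 100%, with the remaining cases read by two tired readers in both arms. A net of 0.5 per 1000 needs h − l = √(2 × 0.5 / (C f)).
- f = 1: gap 0.315 (C = 10.1) or 0.295 (C = 11.5). With l set to match the control rate of 7.8, the offset is 48% or 58%.
- f = 0.25: gap 0.629 or 0.590, offset 0% or 3%. The 0% is a boundary case: h reaches 1 and the control rate cannot be matched.

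So the offset is about 0–58% at gaps of roughly 0.30–0.63.

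**6. What each contrast could show.** Take the ends as 10 of 40 cases: 1,093,780 × 10/40 ≈ 273,000 women. Use C = 10.1 per 1000 and ignore clustering. The pairs are illustrations and are not tuned to the control rate.

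| h / l | Early, late, folded (per 1000) | Power, folded | Power, arm × (reader 1 early vs late) |
|---|---|---|---|
| 0.80 / 0.70 | −0.20, +0.30, +0.05 | 3% | 10% |
| 0.90 / 0.70 | −0.20, +0.61, +0.20 | 8% | 19% |
| 0.60 / 0.40 | −0.81, +1.21, +0.20 | 9% | 86% |
| 0.75 / 0.45 | −0.76, +1.67, +0.45 | 25% | 93% |
| 0.90 / 0.50 | −0.40, +2.02, +0.81 | 60% | 91% |

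For 0.60 / 0.40, the folded difference of 0.202 per 1000 has standard error 0.332, so z = 0.61. The early–late contrast of 2.02 has standard error 0.663, so z = 3.05. The split contrast is the stronger in every row, but for small gaps neither has useful power.

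**The case against.** **The folded stratum answers the question the protocol asks.** Protocol 3.4 speaks of where the intervention may be more effective, which is a net effect. Under the mechanism that net is non-negative, largest at the ends and near zero mid-batch, and the primary analysis averages the same gains and losses over all positions. This stands. A reader might infer that the fold makes the subgroup biased or invalid and that it should be replaced. The documents do not support that.

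**The degree of cancellation is not known.** A reader might also infer that the two ends largely cancel. That holds for small gaps only. No sensitivities are given, and at gaps large enough to deliver the planned effect the offset may be slight. Arbitration, and second readers who can see the first decision, would change the sizes further.

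**Nothing says a null subgroup would be read as no mechanism.** Protocol 3.2 frames the mechanism through recall, arbitration, disagreement and change with time since a break. Order is also analysed unfolded. Supplement 3 reports reader 1 detection by order (OR 0.99987 per case, 0.998–1.001) and reader 1 recall by order (OR 0.9971, 0.9966–0.9977). The absence of a per-case trend in detection means the added test might not have changed the conclusion on detection. These analyses show whether performance drifts along a batch. They contain no arm-by-order term, so they do not show whether reversal moved the peaks.

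**Position may mean place in the list.** If so, and if the four orders are used equally, the two ends are exchangeable and folding loses nothing. This is true, but list position then cannot separate the two effects at all. The wording in Analyses 1 and 3 leaves the matter open, and that Analysis 3 uses the same fold is an inference from its short description.

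**Conclusion.** The point holds as a limitation of the mechanism analysis. The opposite signs follow from the protocol's mechanism and the arm definitions whenever a fresh reader is better than a tired one and neither is perfect. Under independent reads and either-reader detection, the pooled effect is of second order in the sensitivity gap. The early loss offsets about 50–83% of the late gain for assumed gaps of 5–10 points and about 20–33% for 20-point gaps at high sensitivity. At gaps consistent with the planned 0.5 per 1000 it offsets about 0–58%.

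The folded stratum remains a valid test of the net gain at the ends but is a weak test of the mechanism, and no planned analysis supplies the missing contrast. The primary estimate, its error rate and its power are untouched. This is a cheap improvement that should be made, serving a stated secondary aim.

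**What to change.** 1. Keep the folded stratum and label it the net-effect subgroup.
2. In SAP section 3 (Subgroups) and in Analyses 1 and 3, name the reader whose intended order defines position.
3. Add a prespecified treatment × reader 1 intended position term (early, middle, late), derived from R1intendedOrder and batch length, as the secondary mechanism test for cancer detection. State the expected signs: negative early, positive late. Confirm that R1intendedOrder is the place in reader 1's own sequence, as assumed here.
4. Apply the same term to recall and disagreement, without carrying over the detection signs.
5. Amend the blinding text in SAP section 3 so that this one column stays in the blinded dataset. Reader 1's sequence runs from first to last under FF, RR, FR and RF alike, so on its own it does not identify the arm. Reader 2's order should still be removed.

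**Cost.** Some SAP wording and one column derived from a variable the SAP already names. The downsides are one more secondary test and less precise estimates in each split stratum. Since Supplement 3 already reports results, the term would have to be labelled post hoc if it were run on these data now.

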#### Model outcomes

The following variables will be used as model outcomes (see section 6 and 7 for more details).

- Primary: Cancer detected at screen yes / no
- Secondary: Recall Yes/No
- Secondary: Disagreement between readers Yes/No
- Secondary: Health economics: Separate extract

## Details of missing data

- The following variables will be used establish the causation of missing data. Recalled women who did not attend their recall appointment
- Whether the results of her recall appointment/surgery are available
- Missing data counts for all variables considered for inclusion in the model

#### Quality assurance/contamination/protocol violations

Analyses will be conducted as intention to treat unless specified. However, quality assurance measures will also be collected such as contamination of the intervention and protocol violations.

- Contamination: Proportion of cases read in a different order to that intended in the protocol, caused for example by readers moving cases to the end of a batch.
- Contamination: Reader did not complete whole batch in one session. When one reader stops reading batch half way through and come back to it later.
- Non-compliance: Only one reader and not a technical recall
- Non-compliance: More than two readers (means that a trainee has logged in as a real reader, or there were 3 reads)
- Non-compliance: Digital mammography batches or cases read using barcode so not part of the trial
- Non-compliance: Result entered by administrator rather than reader so order is not known
- Non-compliance: Trainee or administrator logs in as a reader and enters results in R1 or R2

#### **Exclusions**

The following cases will be excluded from the analysis

- Technical recall
- Same woman screened twice in 1 year, use only the first screening appointment

#### Other data collection variables

Other to add to database for future exploratory analysis:

- Fully blinded yes/No (from survey of breast screening centres)
- Arbitration method: 1, 2, 3 ormore readers, arbitrate all or disagreements, same people read and arbitrate (from survey of breast screening centres)
- Method of displaying priors (digitise / hang/ available next to workstation) (from survey of breast screening centres)
- Centre size (total number of women in trial in 1 year)
- Number of cases in batch

A separate data extraction will be performed after 3 years to analyse the secondary outcome of interval cancer rate.

#### 4. Data Cleaning

The readers in the NBSS extract will be checked to ensure they are independent readers and not the same person with 2 logins. The number of readers in the NBSS extract will be checked against the number of readers in the survey, and any discrepancies corrected in the survey (including reader type).

A small minority of women may have been screened twice during the data collection period, due to administrative errors, moving GP and rescreen in error, or other rare anomalous reasons. These cases will be identified.

Technical recalls will be counted and removed, missing data, QA and non-compliance will be recoded as per above.

## 5. Descriptive statistics

Table 1. Characteristics of centres taking part in comparison to those not taking part

	Centres taking part (n=47)	Centres not taking part (n=33)
Mean number of women screened in		
one year (sd)		
Mean percentage uptake (sd)		
Mean cancer detection rate (sd)		
Region:		
North East		
North West		
Yorkshire and the Humber		
East Midlands		
West Midlands		
East of England		
London		
South East Coast		
South Central		
South West		

X cases were included in the trial. These were examined by X qualified readers, of which X were radiologists, Y were radiography advanced practitioners and Z were breast clinicians. The mean batch length was X cases (standard deviation y cases)

In X centres arbitration is only when reader 1 and 2 disagree, but in Y centres all recalled cases are arbitrated, even if both reader agree the case should be recalled. A whole range of arbitration methods are used, X centres use one extra reader (third reader arbitration), Y centres use two reader consensus, and Z centres use 3 or more reader consensus.

In X centres the second reader cannot see the first readers decision, in Y centres they cannot see on the computer software but can by looking at the paperwork, and in Z centres the first readers decision is visible onscreen.

All centres taking part in the trial used digital mammography for screening. In X centres the mammograms from the previous screening round were displayed digitally, in Y centres the films were pre-hung on a multiviewer adjacent to the workstation, and in Z centres the film mammograms were available in a screening bag adjacent to the workstation for the readers to hang themselves on a light box if they wished.

Figure 1 Consort diagram

[figure not shown]

Table 2 Descriptive statistics for intervention and control groups (NB these will be group 1 and group 2 until the statistician is unblinded)

	Intervention	Control
Mean age of women screened (sd)		
Mean batch length (sd)		
Cancer detection rate (95%CI)		
Recall rate (95%CI)		
Disagreement rate (95%CI)		

Table 3 Descriptive statistics for reading forwards or backwards

	Forwards	Backwards
Mean time taken per case (sd)		
Reader recall rate (sd)		

#### 6. Statistical Analysis for primary outcome

To determine whether cancer detection rate is higher in the intervention group in comparison to the control group a two-tailed analysis will be conducted using a multi-level logistic regression model in Stata calling MLwiN software. MlwiN will be used because it can compute multi-level models for very large datasets without excessive computer hardware requirements.

Two models will be constructed as detailed below. For all models residuals will be examined for outliers. Analysis will be conducted as intention to treat, with all cases randomised included in the analysis. Missing data through loss to follow up will occur in both groups. This will include women who have been recalled from screening, but either did not attend their follow up appointment or there are no records in the database concerning the results of that appointment. Multiple imputation and sensitivity analysis to examine the effects of any missing data on the model will be considered if missing data is above 5% of the data set. Otherwise complete case analysis will be used.

